## VERSION HISTORY

Version 8.0, 12JUL2022
Amendment to add myocardial strain assessment, global myocardial longitudinal strain (GLS), as one of the primary endpoints.
Version 7.0, 19NOV2020
Amendment to eliminate exclusion criteria #3 - Currently taking GLP-1 receptor agonists . This revision does not increase risk or benefit of study participation as concomitant use of SGLT2 inhibitors and GLP-1 receptor agonists is acceptable clinical practice when indicated. The study randomization will be stratified for use of GLP-1 receptor agonists and statistical analysis will be adjusted for this.
Version 6.0, 17JUN2020
Amendment to extend treatment period, if necessary, to accommodate MR service or Clinical space disruptions due to Public Health Emergency such as COVID-19 Pandemic. Description of this extended treatment has been added to section 4.2.
Version 5.0, 29OCT2019
Amendment to safety monitoring in section 9.2 to include Independent Safety Monitor (ISM) and explicit safety responsibilities for PI, ISM and AstraZeneca in section 6.
Version 4.0, 28MAR2019
Amendment to introduce a time window for Cardiac MRI scans. This is necessary due to challenges in scheduling Randomization, Cardiac MR and Mitochondrial Function Assessment bench time for the same day. Another amendment to change eGFR from <60 to <45 mL/min/1.73 m  as a study exclusion to be in consistent with the updated PI information.
Version 3.0, 12SEP2018
Amendment version for including: (1) a 2-week telephone follow-up visit; (2) study communication plan with study subjects' Primary Providers; (3) abnormal results communications with study subjects' Primary Providers.

## PROTOCOL SYNOPSIS

---

### Effects of SGLT-2 inhibition with dapagliflozin on myocardial fibrosis and inflammation as assessed by cardiac MRI with T1- and T2-mapping in patients with type-2 diabetes

---

#### **Study site(s) and number of subjects planned**

Single center study with 60 subjects enrolled.

Study period		Phase of development
Estimated date of first subject enrolled	Q-3 2018	Study initiation
Estimated date of last subject completed	Q-2 2020	Study completion

#### **Study design**

Randomized, double-blind and placebo controlled cardiac MRI study

#### **Objectives**

Primary Objective:	Outcome Measure:
To investigate whether SGLT-2 inhibition with dapagliflozin will improve myocardial strain performance and reduce progression myocardial fibrosis as assessed by cardiac MRI with T1-mapping in patients with type-2 diabetes.	Extracellular volume fraction (ECV) as assessed by T1-mapping. Myocardial strain measurement

Secondary Objective:	Outcome Measure :
To investigate whether SGLT-2 inhibition with dapagliflozin will reduce myocardial inflammation as assessed by T2-mapping.	T2 relaxation time using T2-mapping

### **Target subject population**

Subjects with type-2 diabetes history  $\geq 5$  years and HbA1C 7-10%

### **Duration of treatment**

One year

### **Investigational product, dosage and mode of administration**

Dapagliflozin 10mg or matching placebo is taken orally once daily in the morning regardless of meals.

### **Statistical methods**

We will assess changes in myocardial strain and ECV, and T2 relaxation time and their variabilities, any signal on treatment effect with dapagliflozin over at least 1 year using an initial sample size of 60 subjects (n=30 in dapagliflozin group and n=30 in placebo group). Assuming a positive treatment effect on ECV with dapagliflozin at 1 year, a planned “interim” analysis will be performed by an independent group, then, lead to an adaption for a sample size reestimation using variability data generated in this initial group. The investigator(s) will be blinded to subject’s treatment status in this process. We will assess the value and feasibility of continuation of the study subject enrollment to reach a sample size suggested by the “interim” analysis and will allowed to include the initial 60 subjects if a larger sample size is needed. On the other hand, if the “interim” analysis indicates no signal of treatment effect on myocardial strain measurement and ECV with dapagliflozin, further study will not be justified.

Given the exploratory nature of the study, we will analyse the data based on if the treatment is truly received, not be limited to intention to treat comparing dapagliflozin with placebo. Furthermore, we will perform the primary analysis based on proportion of time therapy received as needed.

	PAGE
TABLE OF CONTENTS	
TITLE PAGE .....	1
VERSION HISTORY .....	2
PROTOCOL SYNOPSIS.....	3
TABLE OF CONTENTS.....	5
1. INTRODUCTION .....	12
1.1 Background and rationale for conducting this study .....	12
1.2 Rationale for study design, doses and control groups.....	15
1.3 Benefit/risk and ethical assessment.....	16
1.4 Study Design.....	16
2. STUDY OBJECTIVES.....	17
2.1 Primary objective .....	17
2.2 Secondary objectives .....	17
2.3 Exploratory objectives .....	17
3. SUBJECT SELECTION, ENROLMENT, RANDOMISATION, RESTRICTIONS, DISCONTINUATION AND WITHDRAWAL.....	17
3.1 Inclusion criteria .....	18
3.2 Exclusion criteria .....	18
3.3 Subject enrolment and randomization .....	19
3.4 Procedures for handling incorrectly enrolled or randomized subjects.....	19
3.5 Methods for assigning treatment groups.....	19
3.6 Methods for ensuring blinding.....	19
3.7 Methods for unblinding.....	20
3.8 Restrictions .....	20
3.9 Discontinuation of investigational product.....	20
3.9.1 Procedures for discontinuation of a subject from investigational product .....	20
3.10 Criteria for withdrawal.....	20

## LIST OF ABBREVIATIONS AND DEFINITION OF TERMS

### To the Author:

Add terms and abbreviations as required.

Abbreviation or special term	Explanation
T2DM	Type-2 diabetes mellitus
CVD	Cardiovascular diseases
SGLT-2	Sodium-glucose cotransporter-2
ECV	Myocardial extracellular volume
CMRI	Cardiac magnetic resonance imaging
Mit. F	Mitochondrial function
GLS	Global myocardial longitudinal strain

The following abbreviations and special terms are used in this study Clinical Study Protocol.

Abbreviation or special term	Explanation
AE	Adverse event
CRF	Case Report Form (electronic/paper)
CSR	Clinical Study Report
CTCAE	Common Terminology Criteria for Adverse Event
DAE	Discontinuation of Investigational Product due to Adverse Event
DNA	Deoxyribonucleic acid
EC	Ethics Committee, synonymous to Institutional Review Board (IRB) and Independent Ethics Committee (IEC)
GCP	Good Clinical Practice
ICH	International Conference on Harmonisation
International Co-ordinating investigator	If a study is conducted in several countries the International Co-ordinating Investigator is the Investigator co-ordinating the investigators and/or activities internationally.
IP	Investigational Product
IVRS	Interactive Voice Response System

Abbreviation or special term	Explanation
IWRS	Interactive Web Response System
LSLV	Last Subject Last Visit
LIMS	Laboratory information management system
OAE	Other Significant Adverse Event
PGx	Pharmacogenetic research
PI	Principal Investigator
RA	Research Agreement
SAE	Serious adverse event
WBDC	Web Based Data Capture

## 1. INTRODUCTION

### 1.1 Background and rationale for conducting this study

Cardiovascular diseases including atherosclerotic vascular disease and heart failure are the most common complications of type-2 diabetes mellitus (T2DM) and the most prevalent cause of morbidity and mortality in T2DM [1-6]. The exact mechanisms involved in the pathogenesis of cardiovascular diseases (CVD) in T2DM are extremely complex and not entirely clear, however, the increased risk of vascular disease and heart failure in T2DM is not surprising since all 3 conditions share common pathogenetic factors related to metabolic disturbances that result in oxidative stress, low-grade inflammation, activation of RAS system, autonomic neuropathy and impaired calcium homeostasis [2,4]. These pathophysiological responses lead to endothelial dysfunction, atherosclerosis and cardiac fibrosis.

[figure not shown]
Evidence from clinical trials repeatedly confirms the association of T2DM with heart failure, independent of hypertension, atherosclerosis, coronary artery disease [7-9]. It is well established that T2DM patients with heart failure have reduced function capacity [7] and poor clinical outcomes [8] with significantly increased mortality compared with those without heart failure [9]. In addition to the frequent occurrence of coronary artery disease in T2DM, diabetic cardiomyopathy, which is independent of ischemia, also plays important role in development of heart failure [10,11]. Diabetic cardiomyopathy, although the etiology remains unclear, might include a spectrum of dysfunction, as CHF now does, encompassing mild diastolic dysfunction with LV hypertrophy through to a true dilated cardiomyopathy with important systolic dysfunction. Subclinical myocardial dysfunction is even more common than overt heart failure in diabetic patients. TDI, which can be used to estimate longitudinal LV function (shortening of the heart from apex to base), showed reduced LV strain, and impaired systolic and diastolic velocities in 27% of 120 T2DM subjects without overt heart failure, with 16% demonstrating systolic dysfunction alone and 10% both systolic and diastolic dysfunction [12,13]. Longitudinal LV systolic and diastolic dysfunction as ‘early’ diabetic cardiomyopathy might therefore be extremely common [14-16].

Myocardial fibrosis is considered as pathological basis for diabetic cardiomyopathy [17]. Detailed pathological examinations reveal myocardial hypertrophy, interstitial fibrosis, capillary endothelial changes, and capillary basal laminae thickening [18]. Microscopic alterations in small intramural coronary arteries include the narrowing of the lumen due to increased proliferation of endothelial cells, increased thickness of the arteriolar wall due to fibrosis and accumulation of mucopolysaccharides, alterations of elastic fibers, myocytolysis, and perivascular fibrosis [19,20].

Cardiac MRI using T1-mapping is capable of quantifying myocardial extracellular volume (ECV), a surrogate of fibrosis, with excellent inter- and intra-observer variability and could, therefore, be potentially employed for investigations in diabetic myopathy [21]. A recent study [22] showed that ECV by T1-mapping increased as the duration of diabetes increased from 3 to 9 months, consistent with the changes in myocardial fibrosis verified by pathology

[figure not shown]
in diabetic rabbits. Moreover, ECV was strongly correlated with the early diastolic strain rate by Echo ( $r = -0.782$ ,  $p < 0.001$ ). Examples of myocardial fibrosis in dilated cardiomyopathy are shown in **Figures 1-4**. In addition, T2-mapping can help to assess myocardial edema caused by injury and inflammation since the T2 value has been shown significantly higher in the edema area [23,24].

**Figure 1.** Pre- and post-contrast myocardial T1s in normal, interstitial fibrosis and edema.

[figure not shown]

Taylor, A.J. et al. J Am Coll Cardiol Img. 2016; 9(1):67-81.

[figure not shown]
**Figure 2.** Extracellular volume fraction (ECV) by T1-mapping in dilated cardiomyopathy (DCM).

**Figure 3.** Detectable differences in extracellular volume fraction (ECV) by T1-mapping.

**Figure 4.** Prognosis of ECV in DCM.

Assessment of myocardial strain has a robust, independent, and incremental predictive value for incident of heart failure in asymptomatic subjects without any history of previous clinical cardiovascular disease [32]. Cardiovascular magnetic resonance feature tracking (CMR-FT) is a novel technique for non-invasive assessment of myocardial motion and deformation [33] that was described by Hor et al in 2011 [32]. Feature-tracking is an analog of speckle tracking in echocardiographic imaging to follow physiological motion [34]. CMR-FT assesses myocardial strain from routinely acquired cine imaging sequences. Feature-tracking algorithms are designed to focus on border displacement, with a stronger weighing of endocardial deformation. CMR-FT has been already shown the excellent inter- and intra-observer reproducibility of different parameters and at different magnetic field strength [35-37].

In the front of treatment of T2DM, sodium-glucose cotransporter-2 (SGLT-2) inhibition not only offers more effective glucose control but also significant weight loss and reductions in blood pressure. Importantly, EMPA-REG OUTCOME [25] demonstrated that a composite of death from CVD causes, nonfatal MI, or nonfatal stroke occurred in a significantly lower percentage of patients on empagliflozin (490 of 4687, 10.5%) than in the placebo group (282 of 2333, 12.1%, HR: 0.86, 95%CI: 0.74-0.99, P<0.001 for non-inferiority and P=0.04 for superiority). Furthermore, EMPA-REG OUTCOME showed that treatment with empagliflozin compared to standard care was associated with significant reduction in hospitalization for heart failure (HR=0.65, 95%CI: 0.50-0.85, p=0.002). Recently reported CVD-REAL Study [26] in 364,828 patients with T2DM in 6 countries showed that treatment with SGLT-2 inhibitor was associated with significant reduction in hospitalization for heart failure (HR=0.61, 95%CI: 0.51-0.73, p<0.001). It was also significantly associated with lower incidence of all-cause mortality (HR=0.49, 95%CI: 0.41-0.57, P<0.001). The mechanism of improvement in heart failure with SGLT-2 inhibitors is not entirely clear. Animal studies have suggested that SGLT-2 inhibition may improve endothelial function and reduce arterial stiffness, and could attenuate the increase in left ventricle mass and left ventricle end diastolic diameter [27,28]. These findings support a testable hypothesis that SGLT-2 inhibition could reduce myocardial fibrosis and inflammation therefore to improve heart function in T2DM.

In addition, a number of studies have shown mitochondrial dysfunction associated with T2DM. However, it is not clear whether the mitochondrial function assessment using peripheral blood mononuclear cell (PBMC) *in vivo* can reflect specific cell change or damage related to T2DM, for example, myocardial fibrosis to our interest, which is basis for diabetic cardiomyopathy. Another interesting question is whether dapagliflozin can improve mitochondrial function. We propose to address these 2 questions in this study.

## 1.2 Rationale for study design, doses and control groups

Given the unmet needs for CVD risk reduction in patients with T2DM, the promising findings of more effective glucose management and reductions in overall CVD events and hospitalization for heart failure with SGLT-2 inhibition demonstrated in recent trials, and the capability of cardiac MRI with T1- and T2-mapping in assessments of myocardial fibrosis and inflammation, we propose to conduct a staged research program using **adaptive study design**

[29,30] to investigate the effects of SGLT-2 inhibition with dapagliflozin on myocardial strain, fibrosis and inflammation as assessed by cardiac MRI with T1- and T2-mapping in patients with type-2 diabetes.

A total of 60 subjects with  $\geq 18$  years of age, type-2 diabetes history  $\geq 5$  years and HbA1C 7-10% will be randomized at 1:1 to Dapagliflozin 10mg or matching placebo once daily for 1 year. All subjects will be followed every 3 months for clinical and laboratory evaluations and assessments. All subjects will undergo CMRI and mitochondrial function (Mit. F) assessment at baseline and at least 1 year.

[figure not shown]
The primary myocardial strain endpoint includes global myocardial longitudinal strain (GLS). Myocardial fibrosis endpoint is change in extracellular volume fraction (ECV) as assessed by T1-mapping over 12 months. ECV combines native and contrast-enhanced T1 mapping. The change of the T1 relaxation rate (i.e.,  $1/T1$ ) in blood between pre- and post-contrast imaging is converted with the blood hematocrit into a reference for plasma T1, which serves as reference for the T1 changes in tissue as illustrated in **Figure 1**. Endpoint for Mit. F study is monocytes oxygen consumption rates (OCR) using PBMC.

### 1.3 Benefit/risk and ethical assessment

The anticipated benefits and risks of the study will be described in subject informed consent. These will be complete, accurate and consistent with the most recent evaluation of product benefit/risk. The informed consent will be approved by the University of Washington IRB.

### 1.4 Study Design

**Figure 5.** Study flow chart

## 2. STUDY OBJECTIVES

### 2.1 Primary objective

Primary Objective:	Outcome Measure:
To investigate whether SGLT-2 inhibition with dapagliflozin will improve myocardial strain and reduce progression of myocardial fibrosis as assessed by cardiac MRI with T1-mapping in patients with type-2 diabetes.	GLS. Extracellular volume fraction (ECV) as assessed by T1-mapping

### 2.2 Secondary objectives

Secondary Objective:	Outcome Measure :
To investigate whether SGLT-2 inhibition with dapagliflozin will reduce myocardial inflammation as assessed by T2-mapping.	T2 relaxation time using T2-mapping GCS and GRS
To investigate whether SGLT-2 inhibition with dapagliflozin will improve monocytes mitochondrial function.	Oxygen consumption rates (OCR)

### 2.3 Exploratory objectives

Exploratory Objectie:	Outcome Measure :
To investigate whether SGLT-2 inhibition with dapagliflozin will reduce epicardial fat as assessed by CMRI.	Epicardial fat
To examine associations of epicardial fat, myocardial fibrosis and inflammation.	ECV, T2-relaxation time and epicardial fat
To investigate the effects of SGLT-2 inhibition with dapagliflozin on glucose management, LDL particle size and inflammatory markers.	(1) Fasting glucose and HbA1C levels (2) LDL particle size – performed using stored plasma samples. (3) Inflammatory biomarkers include hsCRP, TNF- $\alpha$ and IL-6 – performed using stored plasma samples.

### **3. SUBJECT SELECTION, ENROLMENT, RANDOMISATION, RESTRICTIONS, DISCONTINUATION AND WITHDRAWAL**

Each subject should meet all of the inclusion criteria and none of the exclusion criteria for this study. Under no circumstances can there be exceptions to this rule.

#### **3.1 Inclusion criteria**

For inclusion in the study subjects should fulfil the following criteria based on local regulations:

- (1) Men and women  $\geq 18$  years of age
- (2) Subjects with type-2 diabetes history  $\geq 5$  years
- (3) HbA1C 7-10% with glucose control medications including insulin, metformin or sulfinuria
- (4) Medically stable
- (5) Willing to participate and sign informed consent.

#### **3.2 Exclusion criteria**

Subjects should not enter the study if any of the following exclusion criteria are fulfilled:

- (1) Contraindication to MRI
- (2) Currently or within last three months treatment with a SGLT2 inhibitor
- (3) eGFR  $<45$  mL/min/1.73 m^2
- (4) Unstable or rapidly progressive renal disease
- (5) Hypotension with SBP  $<100$  mmHg
- (6) Hypersensitivity to dapagliflozin or any excipients
- (7) Patients with severe hepatic impairment (Child-Pugh class C)
- (8) Patients with active hepatitis B or C infection
- (9) Any of the following CV/Vascular Diseases within 3 months prior to signing the consent at enrolment, as assessed by the investigator:
- (10) Myocardial infarction
- (11) Cardiac surgery or revascularization (CABG/PTCA)
- (12) Unstable angina
- (13) HF New York Heart Association (NYHA) Class IV
- (14) Transient ischemic attack (TIA) or significant cerebrovascular disease
- (15) Unstable or previously undiagnosed arrhythmia
- (16) Established PAD
- (17) Active bladder cancer
- (18) Recent episode of DKA, frequent episodes of DKA
- (19) High risk of fractures, amputations and fibrosis
- (20) Women of child-bearing potential (ie, those who are not chemically or surgically sterilized or who are not post-menopausal) who have a positive pregnancy test at enrolment or randomization, OR women who are not willing to use a medically accepted method of contraception that is considered reliable in the judgment of the investigator,

from the time of signing the informed consent until two weeks after the last dose of IP, OR women who are breast-feeding.

(21) Individuals with a high risk of fractures, known diagnosis of osteoporosis or osteopenia, and/or history of fracture due to degenerative bone disease.

Procedures for withdrawal of incorrectly enrolled subjects see Section 3.4.

### **3.3 Subject enrolment and randomization**

Investigator(s) should keep a record, the subject screening log, of subjects who entered pre-study screening.

The Investigator(s) will:

1. Obtain signed informed consent from the potential subject before any study specific procedures are performed.
2. Assign potential subject a unique enrolment number.
3. Determine subject eligibility. See Section 3.
4. An unique randomisation code will be assigned to an eligible subject.

If a subject withdraws from participation in the study, then his/he enrolment/randomisation code cannot be reused.

Randomisation codes will be assigned strictly sequentially as subjects become eligible for randomisation.

In addition, randomization will be stratified for RAAS blockade and GLP-1 use in both the treatment and placebo groups.

### **3.4 Procedures for handling incorrectly enrolled or randomized subjects**

Subjects who fail to meet the eligibility criteria should not, under any circumstances, be enrolled or receive study medication. There can be no exceptions to this rule. Subjects who are enrolled, but subsequently found not to meet all the eligibility criteria must not be randomized or initiated on treatment, and must be withdrawn from the study.

Where a subject does not meet all the eligibility criteria but is randomized in error, or incorrectly started on treatment, the Investigator should inform the Sponsor immediately, and a discussion should occur between the Sponsor and the Investigator regarding whether to continue or discontinue the patient from treatment. The Sponsor must ensure all decisions are appropriately documented.

### **3.5 Methods for assigning treatment groups**

A randomization software will be used by a designated investigator to perform the randomization scheme. There will be no stratification factors used in the randomization. This randomization scheme will be linked to study medication dispensing at the University of Washington Investigational Drug Services (IDS).

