# 8. STATISTICAL ANALYSES

## 8.1. Statistical considerations

- All personnel involved with the analysis of the study will remain blinded until database lock and protocol violators identified.
- Analyses will be performed by Principal Investigator or designees.

- Refer to Statistical Analysis Plan for details (if such a document exists and more details will be added).

A comprehensive Statistical Analysis Plan (SAP) will be prepared prior to first subject randomised and any subsequent amendments will be documented, with final amendments completed prior to unblinding of the data (this is the expectation for the pivotal studies).

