## **8.3. Definitions of analysis sets**

### **8.3.1. Efficacy analysis set**

This is primary analysis set for the proposed study and will include any subjects who have both baseline and 1-year follow-up cardiac MRI scans and actually take study medication or placebo.

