### **8.5.1. Analysis of the primary variable (s)**

Ancova test with adjusted for baseline GLS and ECV will be used to compare change in GLS and ECV over 12 months between 2 treatment groups.

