### **8.5.2. Analysis of the secondary variable(s)**

Ancova test will be used for comparisons of changes in secondary endpoints between 2 treatment groups.

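### Sections 3.3 and 3.5 contradict each other on stratified randomisation, and the ANCOVA includes neither stratification factor; the effect on power is probably small and its sign depends on facts not given

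*Combined protocol and SAP*

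**What the plan says.** Four places in the protocol bear on this.

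- Section 3.3 says "randomization will be stratified for RAAS blockade and GLP-1 use in both the treatment and placebo groups".
- Section 3.5, which defines how treatment is assigned, says "There will be no stratification factors used in the randomization".
- Section 8.5.1 gives the primary analysis: "Ancova test with adjusted for baseline GLS and ECV will be used to compare change in GLS and ECV over 12 months". Section 8.5.2 says only that "Ancova test will be used for comparisons of changes in secondary endpoints between 2 treatment groups". Section 8.5.5 lists sensitivity analysis as not applicable. Neither RAAS blockade nor GLP-1 use appears in any analysis section.
- The Version 7.0 entry in the version history says "The study randomization will be stratified for use of GLP-1 receptor agonists and statistical analysis will be adjusted for this". I cite it as a statement of intent only; a difference between an amendment log and current text is not in itself an error.

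Section 8.1 points to a separate analysis plan, but conditionally: "Refer to Statistical Analysis Plan for details (if such a document exists and more details will be added". It puts the last changes to that plan before unblinding, and qualifies this too: "with final amendments completed prior to unblinding of the data (this is the expectation for the pivotal studies".

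**The concern.** A reader cannot tell from the protocol how subjects were allocated. That matters for the analysis, because a model that ignores factors used to balance the arms can misstate its own standard error. Three cases follow, where prognostic means prognostic after the baseline value is in the model.

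1. Stratified allocation, prognostic factors. Balance on the factors reduces the true variance of the treatment estimate, but the unadjusted residual variance still contains the factor effects. The reported standard error is too large, the test is conservative and power is lost.
2. Unstratified allocation, prognostic factors. The unadjusted test is valid. Adjusting helps only if the factors explain more than adjusting costs.
3. Factors not prognostic. Adjusting gains nothing and costs a little.

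At stake is some power in a comparison of 60 subjects, together with a clear record of the allocation scheme and of the model chosen before unblinding.

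**Working it through.** **No figure to reproduce.** Section 8.2 gives 60 subjects, 30 per arm, and says a sample size calculation is not possible. It gives no effect, SD, alpha or power.

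**Inputs.** From the protocol: n = 60, 1:1, ANCOVA on change with baseline. Assumed: two-sided 5% test; effect 0.5 SD; RAAS blockade prevalence 50%, GLP-1 use 20%; R² = share of variance in change, after baseline adjustment, explained by the two factors together, split equally.

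**Approximation at R² = 0.10.** In SD units the standard error is √(2/30) = 0.258, and 0.5/0.258 = 1.936.

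- Stratified, factors omitted: alpha = 2[1 − Φ(1.96/√0.90)] = 3.9%. Power = 1 − Φ((1.96 − 1.936)/√0.90) = 49.0%.
- Factors included: power = Φ(1.936/√0.90 − 1.96) = 53.2%.
- Difference: about 4 points.

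**Simulation.** Stratified means permuted blocks of 4 in the four RAAS × GLP-1 cells; unstratified means a random 30/30 split. There were 20,000 trials per setting (Monte Carlo error about 0.15 points for alpha, 0.35 for power), with all 60 subjects complete.

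| R² | Stratified: alpha, factors omitted | Stratified: power change on adjusting | Unstratified: alpha, factors omitted | Unstratified: power change on adjusting |
|---|---|---|---|---|
| 0 | 5.0% | −0.2 | 5.0% | −1.3 |
| 0.05 | 4.7% | +1.9 | 5.1% | +0.6 |
| 0.10 | 3.9% | +3.9 | 5.2% | +3.0 |
| 0.20 | 3.2% | +9.0 | 4.9% | +7.4 |

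With 15% dropout completely at random, the power changes are −0.2/+1.3/+3.5/+8.4 (stratified) and −1.6/+0.1/+1.9/+6.5 (unstratified). The adjusted model's alpha stays at 4.6% to 5.3% throughout.

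**What these R² values require.** The implied difference between users and non-users is √((R²/2)/(p(1−p))) SD.

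- R² = 0.10: √(0.05/0.25) = 0.45 SD for RAAS and √(0.05/0.16) = 0.56 SD for GLP-1.
- R² = 0.20: 0.63 and 0.79 SD.

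Conversely, a shift of δ SD for each factor gives R² = δ²(0.25 + 0.16). For δ = 0.2, 0.3 and 0.5 this is 0.016, 0.037 and 0.10. In simulation (12,000 trials) adjusting then changes power by +0.6/+1.5/+4.3 points if stratified and −0.9/−0.2/+2.5 if unstratified.

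**Break-even.** Break-even R² = 1 − (mean SE unadjusted / mean SE adjusted)², taken at R² = 0.

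- Stratified: 1 − (0.2596/0.2600)² = 0.003.
- Unstratified: 1 − (0.2593/0.2640)² = 0.035.
- With 15% dropout: about 0.01 and 0.042.

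**Independent check.** Prevalences of 60% and 30% and an effect of 0.72 SD gave the same pattern. Stratified alpha with the factors omitted was 4.8/3.8/3.0% at R² 0/0.10/0.20. Adjusting changed power from 79.1% to 82.1% (stratified) and from 77.7% to 80.6% (unstratified) at R² = 0.10. At R² = 0 it cost 0.2 points (77.8% to 77.6%) and 1.8 points (78.0% to 76.2%).

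**The case against.** The contradiction and the silence of section 8 are not in dispute. The case on the other side concerns their consequences.

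- **Prognostic factors do not guarantee a gain.** A reader might infer that omitting any prognostic factor loses power. Under unstratified allocation that fails below the break-even: at 0.2 SD per factor, adjusting loses about 1 point. This stands.
- **The size is hypothetical.** A reader might take the 9-point figure as the expected loss. It needs factor effects of 0.63 and 0.79 SD after baseline adjustment, which nothing in the documents supports. At 0.2 to 0.3 SD the change lies between −0.9 and +1.5 points. This stands.
- **GLP-1 stratification cannot have applied from the first subject if current users were not eligible.** Version 7.0, dated 19NOV2020, removed the exclusion of current users; enrolment was planned from Q3 2018. Actual enrolment dates are not given. Users may be fewer than 20%, and GLP-1 use is tied to enrolment period. At an assumed 5% prevalence and 0.2 to 0.3 SD, adjusting changes power by +0.2 to +0.5 points (stratified) or −1.2 to −0.6 (unstratified). This stands, and it weakens the power argument further.
- **A separate analysis plan may name the covariates.** A reader might infer that the final analysis will omit them; the documents show only that section 8 does not name them. But section 8.1 leaves open whether such a plan exists, so this does not close the gap.
- **Validity was checked only as randomised.** The primary set "will include any subjects who have both baseline and 1-year follow-up cardiac MRI scans and actually take study medication or placebo", and section 8.5 compares by treatment received. Balance from stratification is not guaranteed there, the conservatism can be weaker, and covariate adjustment does not repair selection into that set. This limits the claim for the fix but does not remove the reason for it.

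**Conclusion.** The point holds in a limited form and should be fixed. Two conclusions need no assumptions: sections 3.3 and 3.5 cannot both be right, and the analysis sections omit both factors that 3.3 says the trial randomises by.

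The statistical consequence is conditional and probably small. With stratified allocation and factors prognostic after baseline adjustment, the unadjusted test is conservative: alpha about 3.9% and about 4 power points lost at an assumed R² of 0.10, or about 1 point at 0.2 to 0.3 SD per factor. With unstratified allocation the test is valid, and adjusting pays only above an R² of about 0.035. All sizes rest on assumed effect, prevalence and prognostic strength.

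A reader might infer from the contradiction that the treatment comparison is biased or that false positives are inflated. Neither follows: in the as-randomised comparison the error from omitting the factors is conservative or nil.

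**What to change.** 1. Reconcile 3.3 and 3.5 to the scheme actually used, and record from which subject GLP-1 stratification applied.
2. Before unblinding, specify in 8.5.1 and 8.5.2, separately for each endpoint: change = treatment + baseline value of that endpoint + RAAS blockade at randomisation (yes/no) + GLP-1 use at randomisation (yes/no), as main effects. Use status at randomisation only, because section 4.2 allows glucose-lowering treatment to be added during the study and later status is post-randomisation.
3. State whether 8.5.1 means each endpoint's own baseline or both the GLS and the ECV baselines in every model. The current wording allows either; the model above takes the first reading.

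In the as-randomised comparison this model holds its type I error under either scheme, so step 2 need not wait for step 1. Selection into the completer, as-treated set needs separate handling.

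Cost: text edits and no new data, since Table 1 already records concomitant medication at screening and baseline. The model spends 2 degrees of freedom (60 − 3 = 57 becomes 60 − 5 = 55 with all subjects complete). If the factors are not prognostic, power falls by about 0.2 to 0.5 points under stratified allocation and by about 1 to 2 points under unstratified allocation.
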